3.3.2.15 GI Perforation/Fistula and Non-GI Fistula Formation

Gastrointestinal perforation/GI fistula: Prior to initiation of treatment with cabozantinib, subjects should be carefully evaluated for potential risk factors including (but not limited to) the following:

- Tumors invading GI or respiratory tracts
- Active peptic ulcer disease, inflammatory bowel disease (eg, ulcerative colitis, Crohn's disease), diverticulitis, cholecystitis or symptomatic cholangitis, or appendicitis
- History of abdominal fistula, GI perforation, bowel obstruction, or intra-abdominal abscess
- Ongoing visceral complications from prior radiation therapy

- Prior GI surgery (particularly when associated with delayed or incomplete healing)
Complete healing following abdominal surgery and/or resolution of intra-abdominal abscess must be confirmed prior to initiating treatment with cabozantinib.

After starting cabozantinib, subjects should be monitored for early signs of GI perforation such as abdominal pain, nausea, emesis, constipation, and fever especially if known risk factors for developing GI perforation or fistula are present.

Discontinue cabozantinib treatment in subjects who have been diagnosed with GI perforation/fistula.

Non-GI fistula formation: Complications from radiation therapy has been identified as a possible predisposing risk factor for fistula formation in subjects undergoing treatment with cabozantinib.

Subjects with any clinically relevant ongoing complications from prior radiation therapy (ie, radiation esophagitis or other inflammation of the viscera) should not be treated with cabozantinib.

Radiation therapy to the thoracic cavity (including mediastinum) should be avoided within 3 months of starting treatment with cabozantinib (excluding local radiation for bone metastases). Fistula should be ruled out as appropriate in cases of onset of severe mucositis or difficulty swallowing after start of therapy. Discontinue cabozantinib and initiate appropriate management in subjects who have been diagnosed with a non-GI fistula.

Discontinue cabozantinib treatment in subjects who have been diagnosed with non-GI fistula.

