3.3.2.14 Hemorrhagic Events

Hemorrhagic events have been reported with cabozantinib. To mitigate risk of severe hemorrhage, subjects should be evaluated for potential bleeding risk factors before initiating cabozantinib treatment and monitored for bleeding events with serial complete blood counts and physical examination while on study. Risk factors for hemorrhagic events may include (but may not be limited to) the following:

- Tumor of the lung with cavitory lesions or tumor lesions which invades, encases, major blood vessels. The anatomic location and characteristics of tumor as well as the medical history must be carefully reviewed in the selection of subjects for treatment with cabozantinib;
- Recent or concurrent radiation to the thoracic cavity;
- Active peptic ulcer disease, inflammatory GI diseases including Crohn's disease and ulcerative colitis;
- Underlying medical conditions which affect normal hemostasis (eg, deficiencies in clotting factors and/or platelet function, or thrombocytopenia);
- Concomitant medication with anticoagulants or other drugs which affect normal hemostasis;
- History of clinically significant hemoptysis.

The risk of hemorrhage in cabozantinib-treated subjects with brain metastases has not been thoroughly analyzed. Though the incidence of CNS hemorrhage events in a study of subjects with GB was higher than observed in general population of subjects with cancer treated with cabozantinib, it is not clear how the risk of hemorrhage in GB translates to a risk of hemorrhage for subjects with brain metastases. Currently, brain metastases of carcinomas are not contraindications to the use of cabozantinib, but subjects with brain metastases should be monitored with a high index of suspicion if symptoms that could be due to a CNS hemorrhage occur.

Complete healing from radiation-induced side effects should have occurred before initiating cabozantinib treatment, and cabozantinib should be discontinued in subjects with serious and life-threatening bleeding events or recent hemoptysis (≥ 2.5 mL of red blood).

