4.2 Exclusion Criteria

A subject who meets any of the following criteria is ineligible for the study:

1. The subject has received cytotoxic chemotherapy (including investigational cytotoxic chemotherapy) or biologic agents (eg, cytokines or antibodies) within 3 weeks, or nitrosoureas/mitomycin C within 6 weeks before the first dose of study treatment;
2. Prior treatment with cabozantinib;
3. Radiation therapy for bone metastasis within 2 weeks, any other external radiation therapy within 4 weeks before the first dose of study treatment. Systemic treatment with radionuclides within 6 weeks before the first dose of study treatment. Subjects with clinically relevant ongoing complications from prior radiation therapy are not eligible;
4. Receipt of any type of small molecule kinase inhibitor (including investigational kinase inhibitor) within 14 days before the first dose of study treatment. Note: Subjects with prostate cancer currently receiving LHRH or GnRH agonists may be maintained on these agents;
5. The subject has received any other type of investigational agent within 28 days before the first dose of study treatment;
6. Known brain metastases or cranial epidural disease unless adequately treated with radiotherapy and/or surgery (including radiosurgery) and stable for at least 4 weeks before the first dose of study treatment. Eligible subjects must be neurologically asymptomatic and without corticosteroid treatment at the time of the start of study treatment;
7. The subject has prothrombin time (PT)/INR or partial thromboplastin time (PTT) test $\geq 1.3 \times$ the laboratory ULN within 7 days before the first dose of study treatment;
8. Concomitant anticoagulation at therapeutic doses with oral anticoagulants (eg, warfarin, direct thrombin and Factor Xa inhibitors) or platelet inhibitors (eg, clopidogrel);

Note: Low-dose aspirin for cardioprotection (per local applicable guidelines), low-dose warfarin (< 1 mg/day), and low dose, low molecular weight heparins (LMWH) are permitted. Anticoagulation with therapeutic doses of LMWH is allowed in subjects

without radiographic evidence of brain metastasis, who are on a stable dose of LMWH for at least 12 weeks before randomization, and who have had no complications from a thromboembolic event or the anticoagulation regimen;

9. The subject has experienced any of the following:
 - a. Clinically-significant GI bleeding within 6 months before the first dose of study treatment;

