14. Major surgery within 12 weeks before the first dose of study treatment. Complete wound healing from major surgery and/or radiation must have occurred 1 month before the first dose of study treatment. Minor surgery (including uncomplicated tooth extractions) within 28 days before the first dose of study treatment with complete wound healing at least 10 days before the first dose of study treatment. Subjects with clinically relevant ongoing complications from prior surgery are not eligible;

15. QTcF > 500 msec within 1 month before the first dose of study treatment:

- a. Three ECGs must be performed for eligibility determination. If the average of these three consecutive results for QTcF is ≤ 500 msec, the subject meets eligibility in this regard.
16. Pregnant or lactating females;
 17. Inability to swallow intact tablets;
 18. Previously identified allergy or hypersensitivity to components of the study treatment formulations;
 19. Diagnosis of another malignancy within 2 years before the first dose of study treatment, except for superficial skin cancers, or localized, low grade tumors deemed cured and not treated with systemic therapy;

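### The minor-surgery sentence in exclusion criterion 14 reads as the reverse of the protocol's own healing requirement, and two radiation rules are not aligned with the safety guidance

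*Combined protocol and SAP*

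**What the plan says.** Section 4.2 opens by making a subject ineligible if any one listed item applies. The synopsis carries the same list. Three rules matter here.

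- **Minor surgery, criterion 14.** The list includes "Minor surgery (including uncomplicated tooth extractions) within 28 days before the first dose of study treatment with complete wound healing at least 10 days" ahead of dosing. Section 3.3.2.7 separately requires surgical and traumatic wounds to be fully healed before the drug is begun.
- **Radiation timing, criterion 3.** The exclusion is "Radiation therapy for bone metastasis within 2 weeks, any other external radiation therapy within 4 weeks before the first dose of study treatment". There is no separate thoracic window, so thoracic radiation other than for bone metastasis falls under the 4-week rule. Section 3.3.2.15 advises: "Radiation therapy to the thoracic cavity (including mediastinum) should be avoided within 3 months of starting treatment with cabozantinib", and adds an exception, "excluding local radiation for bone metastases".
- **Radiation healing.** Criterion 14 states: "Complete wound healing from major surgery and/or radiation must have occurred 1 month before the first dose of study treatment". The bleeding guidance in Section 3.3.2.14 sets a different standard with no interval: "Complete healing from radiation-induced side effects should have occurred before initiating cabozantinib treatment". Criterion 3 also says: "Subjects with clinically relevant ongoing complications from prior radiation therapy are not eligible".

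**The concern.** These rules are there to limit bleeding, fistula and wound complications. The minor-surgery sentence puts what looks like a permission into a list of exclusions, with no word to turn it round. A site that applies it as written turns away the healed patient, and finds nothing in that sentence about the unhealed one.

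The radiation rules raise a lesser question. A patient can pass the exclusion list and still be inside a window that the safety guidance says to avoid, or be unable to meet a healing interval that another criterion demands. Section 2.5 allows up to about 8 sites. If they read these places differently, the enrolled population will vary by site and avoidable eligibility deviations will follow.

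**Working it through.** The plan gives no figure to reproduce. The check sets the rules side by side and counts days. The first dose is day 0. I assume 1 month is about 30 days and 3 months about 90 days.

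**1. Minor surgery.** Take a tooth extraction 20 days before the first dose, which is inside the 28-day window.

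| Wound at first dose | Criterion 14, literal | Criterion 14, read as a permission | Section 3.3.2.7 |
|---|---|---|---|
| Healed for 12 days | Excluded | Not excluded | Met |
| Healed for less than 10 days | Not named | Excluded | Met |
| Not healed | Not named | Excluded | Not met |

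The two readings of criterion 14 give opposite answers in every row. In the last row the literal reading leaves the patient to Section 3.3.2.7. In the middle row Section 3.3.2.7 does not help, because it sets no 10-day interval.

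**2. Thoracic radiation (not local radiation for bone metastases).**
- Criterion 3 (4 weeks = 28 days) is passed if radiation was on day -29 or earlier.
- The Section 3.3.2.15 advice, if it means before the start, covers day -90 onward.
- Overlap: day -90 to day -29, which is 90 - 29 + 1 = 62 days. Radiation 5 weeks before dosing (day -35) is an example.
- If the advice means after the start, it concerns radiation during treatment and there is no overlap with criterion 3. The text does not say which is meant.

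**3. Bone radiation.**
- Criterion 3 (2 weeks = 14 days) is passed if radiation was on day -15 or earlier.
- Criterion 14 needs any wound from radiation to be healed by about day -30.
- For radiation from day -29 to day -15, which is 29 - 15 + 1 = 15 days, a wound cannot have healed by day -30, because the radiation came later than that.
- If the radiation left no wound or injury, both criteria are met. The conflict is therefore conditional, and it turns on what wound healing from radiation covers. The protocol does not define this, and Section 3.3.2.14 speaks of side effects, not wounds.

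**The case against.** The strongest reply has three parts.

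*Entry is governed by the criteria.* Section 5.1 bases eligibility on the inclusion and exclusion criteria, and Section 3.3.2.1 introduces the later sections as management guidelines or precautions. A firm 4-week bar and softer 3-month advice can both be followed. This stands. A reader might infer that the thoracic rules flatly contradict each other, but the advisory wording, the bone exception and the unstated direction do not support that. What remains is a misalignment on a safety matter. Section 3.3.2.14 itself lists recent thoracic radiation as a bleeding risk factor.

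*Criterion 14 concerns wounds.* Time since radiation and time since a wound healed are different quantities and can properly coexist. This also stands. A reader might infer that anyone with bone radiation 3 weeks earlier must fail criterion 14. The text does not support that for a patient with nothing to heal.

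*The intent of the minor-surgery sentence can be guessed, and unhealed patients are guarded elsewhere.* The second half stands: Section 3.3.2.7 requires healing, and criterion 14 separately excludes relevant ongoing surgical complications. A reader might infer that the sentence opens the way to dosing patients with open wounds, and these provisions tell against it. The first half stands only in part. For major surgery, criterion 14 pairs an exclusion window with a separate healing requirement. By analogy, a site could read the minor-surgery sentence as a 28-day bar plus a healing interval, which again excludes the healed patient. Criterion 6 shows that the protocol can write an explicit exception when it wants one. The synopsis repeats the same words and so cannot settle the matter.

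**Conclusion.** The minor-surgery sentence is a clear drafting defect in an operative eligibility rule. Its literal meaning runs against Section 3.3.2.7, and the competing readings decide the same patient differently.

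The two radiation points are secondary. The thoracic gap is about 62 days and exists only if the 3-month advice refers to the period before the start. The bone-radiation gap is about 15 days and exists only where radiation left a wound or injury. Both counts rest on the month lengths assumed above.

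The documents give no number of patients affected. The consequence is inconsistent or wrong eligibility decisions across sites. Nothing here touches the primary endpoint, the 16 + 28 = 44 sample size, the error rates or the two-stage decision rule.

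**What to change.** The sponsor should make these wording changes:

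- Reword the minor-surgery sentence of criterion 14 so that its literal meaning, as an item in an exclusion list, is the intended one. An explicit exception of the kind used in criterion 6 would do this if an exception is what is meant.
- State whether the 3-month thoracic text in Section 3.3.2.15 is advice or an eligibility bar, and whether it refers to radiation before or after the start. Then align it with criterion 3.
- Define what radiation healing covers, and reconcile criteria 3 and 14 with Sections 3.3.2.7 and 3.3.2.14.
- Make every change to the criteria in both Section 4.2 and the synopsis. Editing only one would create a new inconsistency.

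The length of each window and the healing standard are the sponsor's to choose. The cost is the wording of two criteria in two places and of the related guidance paragraphs. No statistical recalculation is needed.

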3.3.2.16 Osteonecrosis of the Jaw

Osteonecrosis of the jaw (ONJ) has been reported in subjects treated with cabozantinib. Additional risk factors for ONJ have been identified including the use of bisphosphonates and denosumab, chemotherapy, corticosteroids, local radiotherapy, and dental or orofacial surgery procedures.

Osteonecrosis of the jaw can manifest as jaw pain, osteomyelitis, osteitis, bone erosion, tooth or periodontal infection, toothache, gingival ulceration, or gingival erosion. Persistent pain or slow healing of the mouth or jaw after dental surgery may also be manifestations of ONJ.

Perform an oral examination prior to initiation of cabozantinib and periodically during cabozantinib therapy as clinically indicated. Advise subjects regarding oral hygiene practice and to quickly report symptoms to investigator. Caution should be used in subjects receiving bisphosphonates.

Invasive dental procedures should be avoided. In cases where dental procedures are unavoidable, treatment with cabozantinib should be held for at least 4 weeks prior to the procedure and resumed after complete wound healing has occurred. Bone healing may often require a protracted time.

If ONJ occurs, cabozantinib treatment should be held and should not be restarted until the condition has sufficiently healed and the Sponsor has approved the re-initiation of therapy.

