2.6 Withdrawals

Subjects may discontinue study treatment or withdraw their consent to participate in the study at any time without prejudice. The investigator may withdraw a subject from study treatment or from the study if, in his or her clinical judgment, it is in the best interest of the subject or if the subject cannot comply with the protocol.

In addition, any of the following conditions require discontinuation of the subject from study treatment:

- An AE or intercurrent illness that in the opinion of the investigator warrants the subject's withdrawal from study treatment;
- The investigator believes it is not in the best interest of the subject to continue study
- Specific conditions described in the Management of Adverse Events Sections 3.3.2 and 3.3.2.1;
- Necessity for treatment with other anticancer treatment prohibited by protocol;
- Sexually active subjects who refuse to use medically accepted barrier methods of contraception (eg, male condom, female condom) during the study and for 4 months after discontinuation of study treatment;
- Women who become pregnant or are breastfeeding;
- If the subject does not recover from his or her toxicities to tolerable Grade ≤ 2 within 6 weeks, the subject will have study treatment discontinued unless there is unequivocal evidence that the subject is benefitting. In this situation, a subject may be able to restart therapy with a dose reduction upon resolution of the toxicity and with agreement of the principal investigator / Sponsor;
- Request by regulatory agencies for termination of treatment of an individual subject or all subjects under the protocol;
- Significant noncompliance with the protocol schedule in the opinion of the investigator;
- The minimum dose of study treatment will be 20 mg once daily (qd). Subjects who cannot tolerate 20 mg qd will have study treatment discontinued;
- Progressive disease (PD) or the subject no longer experiences clinical benefit as determined by the investigator

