3.3.2 Warnings and Precautions and Guidelines for the Management of Adverse Events

The most frequent adverse events experienced by \geq 20% of subjects treated with cabozantinib were diarrhea, fatigue, nausea, decreased appetite, vomiting, weight decreased, PPES, constipation, hypertension, dysgeusia, dysphonia, and asthenia.

Adverse events associated with laboratory abnormalities experienced by \geq 5% of subjects treated with cabozantinib include anemia, AST increased, ALT increased, hypothyroidism, hypokalemia, hypomagnesemia, thrombocytopenia, hypocalcemia, hypophosphatemia, lipase increased, lactate dehydrogenase (LDH) increased, neutropenia, ALP increased, hyponatremia, and leukopenia. Mild to moderate QTc interval prolongation (10-15ms) has also been observed with a QT interval calculated by the Fridericia formula (QTcF) not exceeding 500 ms.

Subjects may also experience medically important but less frequent adverse events including arterial and venous thrombotic AEs (eg, DVT, pulmonary embolism [PE], transient ischemic attack [TIA], and myocardial infarction [MI]), severe hemorrhagic events, proteinuria, wound healing

complications, GI perforation, abscesses including intra-abdominal and pelvic abscess, GI and non-GI fistulae formation, osteonecrosis, and reverse posterior leukoencephalopathy syndrome (RPLS).

Cabozantinib treatment should be permanently discontinued for the following adverse events: visceral perforation or fistula formation, severe hemorrhage, serious arterial thromboembolic events, nephrotic syndrome, malignant hypertension, hypertensive emergency, persistent uncontrolled hypertension despite optimal medical management, osteonecrosis of the jaw (ONJ), and RPLS.

Guidelines for the management of AEs (ie, dose interruptions and dose reductions) are presented in the next sections. Each dose reduction of cabozantinib should be to one dose level lower than the current dose. Dose reductions of more than one dose level are acceptable per Investigator judgment. All AEs should also be managed with supportive care at the earliest signs of toxicity. Adverse reactions are presumed to be attributable to study drug. Adverse events classified as “not related” are defined as AEs that are, without question, not associated with the study treatment and attributable to another cause.

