3.3.2.1 Guidelines for Management of Potential Adverse Events

Sections 3.3.2.2 – 3.3.2.19 present management guidelines or warnings/precautions for the following cabozantinib treatment-emergent adverse events/serious adverse events of interest:

- Gastrointestinal disorders (diarrhea, nausea and vomiting, dehydration [prostate cancer studies], stomatitis and mucositis)
- Hepatobiliary disorders (elevated ALT and AST)
- Hematological disorders

- Fatigue, anorexia, and weight loss
 - Skin disorders (palmar-plantar erythrodysesthesia syndrome [PPES] and rash)
 - Wound healing and surgery
 - Hypertension
 - Thromboembolic events (venous and arterial)
 - Proteinuria
 - QTc prolongation
 - Hypophosphatemia
 - Thyroid function disorders
 - Hemorrhagic events
 - Osteonecrosis of the jaw (ONJ)
 - Angioedema
 - Musculoskeletal and connective tissue disorders
 - Respiratory, thoracic, and mediastinal disorders
-

Please refer to the Investigator's Brochure for additional practice guidelines and management recommendations for these and other AEs potentially related to cabozantinib treatment (e.g. intra-abdominal and pelvic abscess; nervous system disorders; infections and infestations; and respiratory thoracic and mediastinal disorders) use in specific populations, and overdose and first aid measures for accidental cabozantinib exposure.

As with all investigational products, unknown AEs may occur. Subjects should be monitored closely for all AEs. As with other agents in development, additional AEs are unknown.

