≥ 160 mm Hg (systolic) OR ≥ 110 mm Hg (diastolic)	
 Reduce cabozantinib by one dose level^b or interrupt study treatment per investigator discretion Add new or additional anti-hypertensive medications and/or increase dose of existing medications and monitor subject closely for hypotension. If optimized antihypertensive therapy (usually to include 3 agents) does not result in BP < 150 mm Hg systolic or < 100 mm Hg diastolic, study treatment should be dose reduced further or interrupted Study treatment should be dose interrupted if upper limits of systolic BP (≥ 160 mm Hg) are sustained and not adequately manageable or if systolic BP is > 180 mm Hg or diastolic BP > 110 mm Hg, or if subject is symptomatic Re-start study treatment at the most tolerable dose and re-escalate only if BP falls to and is sustained at < 150 mm Hg systolic and < 100 mm Hg diastolic
Hypertensive emergency ^c	
 Discontinue study treatment

BP, blood pressure.

^a The investigator may decide to initiate or adjust antihypertensive treatment at a lower threshold than systolic BP >150 or diastolic BP >100 based on their clinical judgment and assessment of the individual subject.

^b Permitted dose levels are defined by individual protocols.

^c Hypertensive emergency is defined as uncontrolled elevated blood pressure with clinical evidence of progressive or impending end-organ damage (eg, myocardial infarction/ischemia, intracranial hemorrhage, cerebral ischemia, pulmonary edema,

© 2017 AGICC/Criterion Inc.

PROPRIETARY & CONFIDENTIAL

Template Final Ver. 25OCT2017

Protocol 17CRC01/EXELIXIS IST56/Version 2.0 10/27/18

encephalopathy, kidney damage).

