3.3.2.9 Thromboembolic Events

Thromboembolic complications are frequent in cancer patients due to procoagulant changes induced by the malignancy or anticancer therapy including inhibitors of VEGF pathways. Deep vein thrombosis and PE have been observed in clinical studies with cabozantinib; including fatal events (please refer to the Investigator's Brochure). Subjects who develop a PE or DVT should have cabozantinib treatment held until therapeutic anticoagulation with heparins (eg, low molecular weight heparin [LMWH]) is established. LMWH are the preferred management for thrombotic events, warfarin is not recommended. Cabozantinib treatment may be resumed in subjects who are stable and have uncomplicated PE or DVT and are deriving clinical benefit from cabozantinib treatment and that anticoagulation does not place them at a significant risk that outweighs the benefit of resuming treatment per discretion of the investigator/Sponsor. During anticoagulation treatment, subjects need to be monitored on an ongoing basis for bleeding risk and signs of bleeding which may require additional or more frequent laboratory tests in accordance to institutional guidelines. If there are any signs of clinically significant bleedings, cabozantinib treatment should be permanently discontinued.

Arterial thrombotic events (eg, transient ischemic attack, myocardial infarction) have been observed in studies with cabozantinib. Subjects should be evaluated for preexisting risk factors for arterial thrombotic events such as diabetes mellitus, hyperlipidemia, hypertension, coronary artery disease, history of tobacco use, and cardiac or thromboembolic events that occurred before initiation of study treatment. Cabozantinib treatment should be discontinued in subjects who develop an acute myocardial infarction, cerebral infarction or any other clinically relevant arterial thromboembolic complication.

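### Osteonecrosis of the jaw calls for permanent discontinuation in Section 3.3.2 but for a hold with possible restart in Section 3.3.2.16, and no rule says which text governs

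*Combined protocol and SAP*

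**What the plan says.** **ONJ.** Section 3.3.2 opens a list with "Cabozantinib treatment should be permanently discontinued for the following adverse events". The list ends with "persistent uncontrolled hypertension despite optimal medical management, osteonecrosis of the jaw (ONJ), and RPLS". ONJ carries no grade, severity or healing condition there.

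Section 2.6 lists conditions that require a subject to come off study treatment. One entry is "Specific conditions described in the Management of Adverse Events Sections 3.3.2 and 3.3.2.1".

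Section 3.3.2.16 gives a different instruction: "If ONJ occurs, cabozantinib treatment should be held and should not be restarted until the condition has sufficiently healed". Its second condition for restart is that "the Sponsor has approved the re-initiation of therapy".

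**QTcF.** Section 3.3.2.11 requires treatment to be withheld, and the Sponsor notified at once, when the average of three ECGs is above 500 ms or more than 60 ms above baseline. Restart at a reduced dose needs every one of five listed conditions. One is that the excess was not confirmed under the protocol's procedures.

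**Missed dose.** Section 3.2 allows a missed dose to be taken up to 12 hours late. The subject directions in the drug diary (Appendix B) tell subjects not to make up missed doses.

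**The concern.** A subject cannot be both permanently off treatment and eligible to restart after healing. A site working from Section 3.3.2 stops for good and has no reason to ask the Sponsor anything. A site working from Section 3.3.2.16 holds treatment and may ask to restart. Both would be following the protocol.

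At stake are subject safety and uniform conduct across the up to about 8 sites in Section 2.5. Exposure and the recorded reasons for discontinuation could also differ between sites for the same event.

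The QTcF list raises a similar worry. If its confirmation condition refers to the ECG average that triggered the hold, no subject held under that step could ever meet the list.

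**Working it through.** The plan has no figure of its own to reproduce here. The check sets the texts side by side, then bounds how often ONJ might arise.

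**1. ONJ instructions**

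| Place | Instruction | Severity limit | Restart |
|---|---|---|---|
| Section 3.3.2 | Permanent discontinuation | None | No |
| Section 2.6 | Specific conditions in Sections 3.3.2 and 3.3.2.1 require discontinuation | None of its own | Not addressed in that entry |
| Section 3.3.2.16 | Hold | None | After sufficient healing and Sponsor approval |

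The first and third rows cover the same event and cannot both be followed. A severity split could have reconciled them, but neither text has one. No sentence says that the general list overrides the event sections, or the reverse.

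**2. How far sites could diverge**

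- Section 3.3: if an interruption for related adverse events exceeds 6 weeks, cabozantinib should be discontinued unless the subject is unequivocally benefitting. Section 2.6 has a similar six-week rule based on recovery from toxicity.
- Section 3.3.2.16 itself warns that bone healing can be slow. Many related ONJ holds could therefore pass 6 weeks and default to discontinuation.
- What remains open: holds that end within 6 weeks, subjects with unequivocal benefit, and, under Section 3.3, interruptions for events judged unrelated. Restart under Section 3.3.2.16 still needs Sponsor approval.

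**3. How often ONJ might arise**

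The documents give no ONJ rate. Table 1-4 lists serious adverse events in at least 1% of 2410 subjects, and ONJ is not on it. Assume that serious ONJ is below 1% and that the pooled rate carries over to this trial:

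- Expected serious cases in 44 subjects: below 44 × 0.01 = 0.44.
- Probability of at least one: below 1 − 0.99^44 = 1 − 0.643 = 0.357.

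Non-serious ONJ is bounded only loosely. Table 1-3 lists events in at least 10% of subjects and ONJ is absent, so the expected number of cases of any kind is below 44 × 0.10 = 4.4. These are upper limits, not estimates. Section 3.3.2 describes osteonecrosis as less frequent.

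**4. QTcF restart list**

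Let C mean that the three-ECG average is over the threshold. The withhold step requires C. Restart requires all five conditions, one of which is that the excess is not confirmed.

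- If confirmation means the three-ECG average, that condition is not-C. C and not-C cannot both hold, so nobody held under this step could restart.
- If confirmation means the hourly repeat triplicates, which the same section also orders, the condition may be attainable.

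The term is undefined, so the text does not choose. Two other conditions (a week's wait after QTcF returns to range, and a cause other than cabozantinib) and the ECG schedule after reinitiation assume that a real prolongation can be followed by restart.

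Scope is also unclear. The list follows a sentence about subjects with prolongation and symptoms, and its first condition concerns symptoms. If it covers only those subjects, asymptomatic ones fall to Section 3.3.1.1, which has no one-week wait and no Sponsor agreement for restart. The Sponsor must still be notified in every case over the threshold, but notification is not agreement.

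**5. Missed dose**

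Section 3.2 is permissive. A subject who follows the diary complies with both texts. Only one who takes the late dose within the 12 hours departs from the diary.

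**The case against.** **The specific section governs the general list.** This is the natural defence, but the documents do not state it, and comparison with other listed events points both ways. For hypertensive emergency, Table 3-6 repeats the list ("Discontinue study treatment"). For arterial events, Section 3.3.2.9 does too: "Cabozantinib treatment should be discontinued in subjects who develop an acute myocardial infarction, cerebral infarction or any other clinically relevant arterial thromboembolic complication". For sustained, poorly controlled hypertension, however, Table 3-6 works through reduction, interruption and restart, which is arguably softer than the list. The pattern supports no precedence rule in either direction.

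**Section 2.6 is neutral because it brings in both ONJ texts.** A reader might infer this, since Section 3.3.2.1 says that the later sections "present management guidelines or warnings/precautions for the following cabozantinib treatment-emergent adverse events/serious adverse events of interest". But the Section 2.6 list covers conditions that require discontinuation, and a hold with restart is not one. Only the Section 3.3.2 entry fits, so Section 2.6 sharpens the conflict. It still does not say that Section 3.3.2.16 is displaced.

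**The practical gap is small.** Much of this stands. The six-week rule, Sponsor approval and probable rarity all limit it. They do not tell a site which instruction to follow on the day ONJ is diagnosed.

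**The QTcF rule makes restart impossible.** This stronger reading is tempting but not established. It depends on equating an undefined term with the triggering average, and the hourly triplicates are a possible alternative. The trigger may also be rare: Section 3.3.2.11 reports a mean rise of 10 to 15 ms at 140 mg daily and no treated subject above 500 ms. It gives no rate for rises above 60 ms.

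**Conclusion.** The ONJ conflict is real and should be fixed. Two sections give incompatible instructions for the same unqualified event, and nothing ranks them. Confidence in this is high, since it rests on the wording alone. The practical size is limited: Sponsor approval and the six-week rule narrow the divergence, and serious ONJ is probably uncommon, if the pooled safety data carry over to this trial.

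The QTcF point is secondary and less certain. What is shown is an undefined term and an unclear scope. It becomes a contradiction only if the triggering three-ECG average is the confirmation step.

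The missed-dose difference is minor because Section 3.2 only permits the late dose.

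A reader might infer that the trial's conclusions are at risk. The documents do not support that: the sample size, the Simon decision rule and the primary analysis do not depend on these texts.

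**What to change.** 1. Reconcile Sections 3.3.2 and 3.3.2.16, together with the cross-reference in Section 2.6, so that one ONJ instruction remains, or state which section takes precedence.
2. In Section 3.3.2.11, define what counts as confirmation and state whether the restart list covers asymptomatic subjects or Section 3.3.1.1 does, so that the list is consistent with the withhold step.
3. Align the diary directions in Appendix B with Section 3.2.

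The clinical content of each rule is for the sponsor and investigator to decide.

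The cost is one wording amendment, with the company review and IRB/EC approval that Section 13 requires, distributed to up to about 8 sites, plus a revised diary page. Nothing in the design or analysis changes.
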